3.3 Hypothesis

H_0 = The Humylub Ofteno® PF ophthalmic solution is not inferior in its efficacy compared to its comparators, after 30 days of treatment, presenting a 35% decrease in the final score of the OSDI test compared to its initial value in at least 30% of exposed patients.

$$H_0: P_A - P_B \leq \delta$$

H_1 = The Humylub Ofteno® PF ophthalmic solution is inferior in its efficacy compared to its comparators, after 30 days of treatment, as it does not present a 35% decrease in the final score of the OSDI test compared to its initial value in at least 30% of exposed patients.

$$H_1: P_A - P_B > \delta$$

4. Study design

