10.2.2 Justification for sample calculation

Sample size calculation was performed based on the results of the phase IV, multicenter, prospective, double-blind, randomized efficacy and safety clinical study of Humylub Ofteno® PF ophthalmic solution, versus Systane® Ultra and Systane® Ultra preservative free performed in subjects diagnosed with mild to moderate dry eye. The reduction in the mean score of the OSDI test was considered as the main efficacy variable, with a dosage of 1 drop QID. In this study, after one month of treatment, subjects assigned to Humylub Ofteno® PF had a decrease of -49.3% vs -41.3% for Systane Ultra and -48.3% for Systane Ultra PF, with respect to their initial mean values with no statistical differences between treatments ($p>0.05$) [57].

For the present protocol, it is expected that, after 3 days of treatment, 30% of subjects treated with Humylub Ofteno® PF will have a 35% decrease in OSDI score compared to their initial mean value.

The sample size was calculated using the equation for two proportions [58], considering a power of 80% (β), a significance level of 0.05 (α) and a margin of non-inferiority (δ) of 10% and based on the following working hypotheses:

$$H_0: P_A - P_B \leq \delta$$

$$H_1: P_A - P_B > \delta$$

Where, δ is the margin of non-inferiority and, the ratio between the sample size of the two groups is:

$$k = \frac{\eta A}{\eta B}$$

Equations

The calculation to estimate sample size and power was performed using an online tool and following the equations: [59]

$$n_A = kn_B \text{ y } n_B = \left(\frac{P_A(1 - P_A)}{k} + P_B(1 - P_B) \right) \left(\frac{z_{1-\alpha} + z_{1-\beta}}{p_A - p_B - \delta} \right)^2$$

$$1 - \beta = \Phi(z - z_{1-\alpha}) + \Phi(-z - z_{1-\alpha}) \text{ , } z = \frac{P_A - p_B - \delta}{\sqrt{\frac{P_A(1 - P_A)}{n_A} + \frac{P_B(1 - P_B)}{n_B}}}$$

$$k=nA/nB$$

Φ is the standard normal distribution function

Φ^{-1} is the standard normal quantile function

α is a Type I error,

β is the Type II error, which means that $1-\beta$ is the power, and

δ is the test margin.

According to the previous calculation, the result was 50 subjects, this calculation was increased by 20% considering possible losses (10 subjects). The total suggested sample size is 180 subjects (60 cases per arm), which will provide both eyes for the study.

11. Ethical considerations

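### Section 3.3 states two incompatible non-inferiority rules: in words a Humylub-only responder floor, in symbols a comparison with an unsigned margin and reversed labels

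*Combined protocol and SAP*

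**What the plan says.** Section 3.3, repeated in the synopsis, words H0 as Humylub being not inferior to its comparators after 30 days, "presenting a 35% decrease in the final score of the OSDI test compared to its initial value in at least 30% of exposed patients". H1 words inferiority as missing the same mark: "as it does not present a 35% decrease in the final score of the OSDI test" in that share of patients. Each sentence is followed by a symbolic statement. For H0 it is "H_0: P_A - P_B \leq \delta", and for H1 the reverse inequality. Section 3.3 does not say which products A and B are, and δ carries no sign.

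Section 10.2.2 uses the same 30%/35% pair as a planning assumption: "after 3 days of treatment, 30% of subjects treated with Humylub Ofteno® PF will have a 35% decrease in OSDI score". It adds 80% power, α 0.05 and a 10% margin, and arrives at 50 per arm, raised to 60 for losses. No comparator rate is given. The data cited in support come from an earlier one-month result in which "subjects assigned to Humylub Ofteno® PF had a decrease of -49.3% vs -41.3% for Systane Ultra and -48.3% for Systane Ultra PF". These are falls in group mean scores, and the section reports that the three products did not differ significantly.

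Section 10.1.2 repeats the 10% margin without a scale and plans repeated-measures ANOVA or a t test between groups. The variable table in 7.4.4 treats OSDI as a continuous score. Neither section compares a confidence limit with the margin.

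**The concern.** Non-inferiority is a statement about a difference from a comparator. The only success criterion spelled out in words is a property of one arm. It would label Humylub not inferior at 30% responders whatever Hyabak or Lagricel achieved. It would also label Humylub inferior at 28% responders against 20% on a comparator.

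The symbols do not settle the matter. In 10.2.2 the planned proportion is a response rate. If A is Humylub, a small or negative P_A − P_B is then bad for Humylub, yet that is the side labelled not inferior. The statement to be demonstrated has also been placed in the null hypothesis.

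The analysis sections supply no margin-based test to fill the gap. A final report could therefore claim non-inferiority from a single-arm result. Section 11.3 lists achievement of the primary objective among the grounds for early termination, so an ambiguous rule could affect conduct as well as reporting.

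**Working it through.** **1. The plan's own sample size.** The equation in 10.2.2 is n = [P_A(1−P_A) + P_B(1−P_B)] × [(z at 1−α + z at 1−β)/(P_A − P_B − δ)]², with k = 1. The stated inputs are P_A = 0.30, margin 0.10, α = 0.05 (one-sided, since the equation uses 1−α) and power 0.80. P_B is not stated.

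- Assuming P_B = P_A = 0.30 and δ = −0.10: 0.42 × (2.4865/0.10)² = 0.42 × 618.3 = 259.7, so **260 per arm**, not 50. At one-sided 0.025 it is 330.
- With P_A = 0.30 and δ = −0.10, a result of 50 appears if P_B is about 0.19, meaning Humylub is assumed 11 points better. It also appears if 0.493 and 0.35 are entered as the two proportions. Both are guesses; the document records neither.

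**2. What the planned size delivers under a relative rule.** Power ≈ Φ(0.10/SE − 1.645), with SE = √(2p(1−p)/n), for each comparison. At p = 0.30:

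- n = 50: SE = 0.092, power 0.29.
- n = 60: SE = 0.084, power 0.33.

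A higher common rate does not rescue this. With 60 per arm, power is 0.29 at 50% response, 0.31 at 65% and 0.33 at 70%. For 80% power the equation gives 310, 282 and 260 per arm respectively.

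**3. The floor against a relative rule.** The floor is read as an observed share of at least 30%, so 18 or more of 60. The relative rule is a one-sided 95% Wald lower limit above −0.10, by exact enumeration with 60 per arm. The true rates are assumptions, because the documents give no responder rate for either comparator.

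| True response, Humylub / comparator | Floor met | Lower limit above −0.10 |
|---|---|---|
| 40% / 70% | 0.96 | 0.0001 |
| 35% / 50% | 0.83 | 0.016 |

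**4. The printed symbols, read literally.** For 40% against 70%, P_A − P_B = −0.30. This is at or below δ whether δ is +0.10 or −0.10, so the printed H0, labelled not inferior, is true of a product 30 points worse.

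**5. The 30% rate beside the 49.3% fall.** One is a share of patients and the other a fall in the group mean. Even for individual falls capped at 100%, 30% responders allow a mean of up to 0.30 × 100 + 0.70 × 35 = 54.5%. Conversely, a 49.3% mean needs only (49.3 − 35)/(100 − 35) = 22% responders. There is no arithmetical contradiction. If individual falls were roughly normal around 49.3%, the share reaching 35% would be Φ((49.3 − 35)/SD): 83% at SD 15, 68% at SD 30, 61% at SD 50 and 57% at SD 80. The SDs are assumed; the documents give none.

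**The case against.** The strongest reply is that a comparison does exist. The H0 sentence refers to the comparators, P_A − P_B against δ is printed beneath it, the primary objective in 3.1 is comparative, and a 10% margin appears in the synopsis, 10.1.2 and 10.2.2. On this view the 30%/35% pair is a planning expectation that strayed into the hypothesis. This stands in part: a reader who inferred that the trial has no comparative rule at all would be going too far. But the worded criterion is attached to both hypotheses in both places, the symbols carry reversed labels and an unsigned δ, and the analysis sections do not apply the margin.

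A reader might also infer that the 30% floor contradicts the earlier 49.3% fall. The documents do not support that, because the two quantities differ and can coexist (step 5). A fall in a group mean also weights patients by baseline. For example, with assumed baselines, let 30% of patients start at 32 and fall 72%, and 70% start at 13 and fall 25%. The mean then drops from 18.7 by 9.19, or 49.1%, with 30% responders. The normal-model rates are only indicative: a normal curve places some patients above the possible 100%, and the SD is unknown. What can be said is that 30% looks low and the plan does not explain it.

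The 3-day timing is probably a slip, since 3.3 says 30 days and the cited data are at one month. It needs only to be reconciled.

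**Conclusion.** The point holds as an inconsistency between the worded and symbolic hypotheses, with a worded rule that cannot establish non-inferiority. The reversed labels, undefined A and B, unsigned δ and missing margin-based test can be read from the text and need no assumption. The probability of 0.96 rests on assumed rates of 40% and 70%, 60 evaluable patients per arm, and reading the floor as an observed proportion.

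The low 30% rate and the mismatch between 3 and 30 days are secondary: they are unexplained, but neither contradicts the earlier study's result. It would also be wrong to infer that rewording leaves the sample size untouched. Once the comparison governs, 50 per arm is not supported by the stated inputs under equal rates, and the stated 80% power becomes about 29% to 33% per comparison at 30% response.

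**What to change.** - **Synopsis and 3.3:** delete the clause requiring 30% of patients. Define a responder as a patient whose OSDI at the final visit is at least 35% below their own baseline. For each comparator, state H0: P_Humylub − P_comparator ≤ −0.10 and H1: P_Humylub − P_comparator > −0.10.
- **7.4.4 and 10.1.2:** add the responder variable. Conclude non-inferiority only if the lower confidence limit of the difference in responder proportions exceeds −0.10. Give the margin its scale (percentage points of responders).
- **10.2.2:** reconcile 3 days with 30 days. State the assumed comparator rate. Replace the assumed 30% with the one-month 35%-responder rate tabulated from the earlier study's patient-level data. Restate the power that the planned size delivers.

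The wording changes and one tabulation from a study the sponsor ran cost little. The real cost is that the stated power becomes much less favourable. The sponsor must then either report that power openly or enlarge the trial, to about 260 per arm if 80% is wanted at equal 30% rates and one-sided 0.05.

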4.1 Design Overview

Phase IV non-inferiority, controlled, open-label, comparative, multicenter clinical study.

4.2 Rationale for the study design

Humylub Ofteno® PF is a product that is currently available for consumption not only in Mexico, but in several Latin American countries such as: Bolivia, Chile, Colombia, Costa Rica, Costa Rica, Colombia, Costa Rica, Colombia Dominican Republic, Ecuador, Guatemala, Haiti, Honduras, Nicaragua, Panama and El Salvador.

Both the efficacy and safety of its compounds, HS and CS, have been proven for use as a treatment for SOS, reducing both the signs and symptoms associated with this pathology. There are several ophthalmic solutions on the market that contain these compounds, including the comparators chosen for this study, Hyabak® and Lagricel® PF. The latter are composed of sodium hyaluronate, at different concentrations, and are also used for the treatment of SOS. One of the main purposes of SOS treatment is to reduce the symptoms described by patients such as burning, SCE, blurred vision, etc. The objective evaluation of these is carried out through internationally approved and accepted questionnaires, which are described in reference documents such as the TFOS DEWS II. One of these tools is the OSDI, the results of which will be considered in this study as the primary outcome variable. Like most efficacy studies for lubricating eye solutions, assessing improvement in patient-reported symptoms compared to reference products is the primary objective of this study. [36]

Due to the differences in the presentation of Humylub Ofteno® PF with one of its comparators, Hyabak®, and thanks to the characteristics of its bottles, this will be an open-label study.

Finally, considering the evaluation of the secondary variable of TRL efficacy by means of a non-invasive method, and since the equipment required to carry out this assessment is not so widely disseminated in ophthalmological offices and clinics in general, multiple research centers will be in charge of executing this study.

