6.1 Managed Products

6.1.1 Investigational Product

- Generic name: Sodium hyaluronate / Chondroitin sulfate.
- Distinctive name: Humylub Ofteno® PF.
- Active ingredients: Sodium hyaluronate 0.1% / Chondroitin sulfate 0.18%.
- Pharmaceutical form: Ophthalmic solution.
- Presentation: multi-dose dropper bottle, 10 mL.
- Prepared by: Laboratorios Sophia, S.A. de C.V.
- Solution description: Transparent solution, free of visible particles.
- Packaging description: White bottle made of low-density polyethylene with system Novelia® filled to 10 mL.

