6.1.2 Reference product

- Generic name: 0.15% sodium hyaluronate.
- Distinctive name: Hyabak®.
- Active ingredients: Sodium hyaluronate 0.15%.
- Pharmaceutical form: Ophthalmic solution.
- Presentation: multi-dose dropper bottle, 10 mL.
- Prepared by: *Laboratoires Théa*, Clermont-Ferrand, France.
- Solution description: Transparent solution, free of visible particles.
- Packaging description: Abak® multidose bottle of 10ml.
- Generic name: Sodium hyaluronate
- Distinctive name: Lagricel Ofteno® PF.
- Active ingredients: Sodium hyaluronate 0.4%
- Pharmaceutical form: Ophthalmic solution.
- Presentation: multi-dose dropper bottle, 10 mL.
- Prepared by: Laboratorios Sophia, S.A. de C.V.
- Solution description: Transparent solution, free of visible particles.

- Packaging description: White bottle made of low-density polyethylene with Novelia system® filled to 10 mL.

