6.1.2.1 Justification of the reference product

Hyabak® is a preservative-free lubricant manufactured by Théa Laboratories, which is indicated for the treatment of SOS. [37] It is composed of 0.15% HS and is packaged in a multi-dose bottle. It is currently a direct commercial competitor of Humylub Ofteno® PF and Lagricel Ofteno® PF.

As it is composed of HS, it shares with the products of Laboratorios Sophia, S.A. de C.V. already mentioned, some of the benefits that it can offer to patients diagnosed with SOS. However, it lacks the association with CS as in the case of Humylub Ofteno® PF, and the properties attributed to a higher concentration of HS, as in Lagricel Ofteno® PF.

On the other hand, Lagricel Ofteno® PF is an ocular lubricant also manufactured by Laboratorios Sophia, S.A. de C.V. It has a broad safety profile from its development phase to the pharmacovigilance to which it has been subjected since its international commercialization, both in its single-dose presentation and in its multi-dose version, both free of preservatives.

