7.3 Randomization

Randomization of subjects will be carried out using a computer-based assignment system. After signing the FCI, the patient will receive a patient number with which all their information will be encrypted pseudonymity during collection and completely anonymized during analysis.

The containers will be identified by means of labels, which, in accordance with current and applicable regulations, must contain at least:

1. Sponsor's name, address, and phone number.
2. Dosage form and route of administration.
3. Batch number.
4. Legend "For clinical studies only"
5. Expiration date.

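### Section 4.2 makes all three arms open label for a reason that names only Hyabak; nothing stated prevents masking Humylub against Lagricel, one of the two primary comparisons

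*Combined protocol and SAP*

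**What the plan says.** The design statement in 4.1 reads "Phase IV non-inferiority, controlled, open-label, comparative, multicenter clinical study". The reason comes in 4.2: "Due to the differences in the presentation of Humylub Ofteno® PF with one of its comparators, Hyabak". The same sentence adds a general remark about the characteristics of the bottles. Lagricel is not mentioned in it.

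The product descriptions are in 6.1:

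- Humylub (6.1.1): "Prepared by: Laboratorios Sophia, S.A. de C.V"; "White bottle made of low-density polyethylene with system Novelia® filled to 10 mL".
- Lagricel (6.1.2): "White bottle made of low-density polyethylene with Novelia system® filled to 10 mL". Section 6.1.2.1 adds "Lagricel Ofteno® PF is an ocular lubricant also manufactured by Laboratorios Sophia, S.A. de C.V".
- Hyabak (6.1.2): "Packaging description: Abak® multidose bottle of 10ml".

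All three solutions are described as transparent and particle-free. The synopsis gives all three the same regimen, and 6.1.3.1 says the two sponsor products share the same labelled interval.

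Under 7.3, assignment is computer-based, and "The containers will be identified by means of labels". The minimum label content listed there includes batch number and expiry date but not the product name.

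The primary variable is the OSDI (7.4.1), a self-administered symptom questionnaire (7.4.4.2). Staining is graded on the Oxford scale and hyperemia on the Efron scale by direct observation (7.4.4). No masked assessor is described.

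**The concern.** A patient who knows which drop was assigned may answer a symptom questionnaire differently, and an examiner who knows may grade a borderline stain differently. If that happens to a different degree in the two arms being compared, the estimated difference shifts by an amount the analysis cannot separate from a treatment effect. In a non-inferiority trial a shift towards the test product can produce a false claim, and a shift away from it can hide true non-inferiority.

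Open label is a reasonable choice where products cannot be made to look alike. Here the stated obstacle belongs to one comparator, but its consequence has been applied to both. The primary objective (3.1) compares Humylub with Hyabak and with Lagricel, so one of two primary comparisons is left open without a reason of its own.

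**Working it through.** The point rests on comparing sections, not on a figure in the plan.

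**Does the stated reason reach Lagricel?**

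| Feature | Humylub | Lagricel | Hyabak |
|---|---|---|---|
| Maker | Sponsor | Sponsor | Another company |
| Bottle | White LDPE, Novelia, 10 mL | White LDPE, Novelia, 10 mL | Abak, 10 mL |
| Solution | Transparent | Transparent | Transparent |
| Trial regimen | Same | Same | Same |
| Active content | Hyaluronate 0.1%, chondroitin 0.18% | Hyaluronate 0.4% | Hyaluronate 0.15% |

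On bottle and maker, Hyabak differs and the other two match as described. The regimen would not reveal the arm. The one listed difference between Humylub and Lagricel that a patient might notice is the formulation, and 4.2 does not cite it.

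**Are the means available?** Trial labels and a computer-based assignment system are already planned (7.3). The adverse-event record in 8.4.1 already allows a product code and refers to opening a blind. The sponsor's earlier phase IV trial of Humylub against another maker's products is described in 10.2.2 as double-blind.

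**What could a bias do?** The documents give no bias size, so this is an illustration on assumed values. Inputs from 10.2.2: margin 0.10, alpha 0.05 (taken as one-sided), 60 per arm (50 before the allowance for losses), and a 30% response rate. The plan states that rate for Humylub; it is used here for the comparator, pB = 0.30. Let pA be the observed Humylub response rate, including any bias. Then

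P(declare non-inferiority) = Φ{ (pA − pB + 0.10) / √[pA(1−pA)/n + pB(1−pB)/n] − 1.645 }

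Take a true Humylub rate of 0.20, exactly at the margin, and add a bias b in its favour. For b = 0.05 and n = 60: pA = 0.25; standard error = √[(0.1875 + 0.21)/60] = 0.0814; 0.05/0.0814 = 0.614; 0.614 − 1.645 = −1.031; Φ = 0.151.

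| Assumed bias towards Humylub | pA | n = 60 | n = 50 |
|---|---|---|---|
| 0 | 0.20 | 5% | 5% |
| 3 points | 0.23 | 10% | 10% |
| 5 points | 0.25 | 15% | 14% |
| 10 points | 0.30 | 33% | 29% |

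Because the formula depends only on the observed rates, the table also serves the opposite direction. If the true rates are equal at 30%, a bias of 0, 5 or 10 points against Humylub gives pA = 0.30, 0.25 or 0.20. With 60 per arm the chance of showing non-inferiority is then 33%, 15% or 5%. (That the starting value is only 33% is a separate sample-size matter.)

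**The case against.** The strongest case for leaving the design alone is that open label is disclosed and reasoned, and that mixed masking within one three-arm randomisation has its own interpretive cost. Several parts of this case stand.

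- **The bottles are described alike, not shown to be identical.** Colour, material, dispensing system and volume match, but caps and printing are not described. A reader might infer that masking would be complete and its absence needless. The documents do not go that far: hyaluronate 0.4% against 0.1% plus chondroitin may feel different on instillation.
- **The direction of bias is unknown.** A reader might infer that open label favours Humylub. Both products are the sponsor's, and 6.1.2.1 credits Lagricel with properties of a higher hyaluronate concentration, so expectation could run against Humylub. The competitor comparison, where commercial interest is plainer, stays open under the fix.
- **Masking does not remove expectations shared by both arms.** It addresses only differential expectation and differential grading.
- **The label list is a minimum.** Omitting the product name from it does not mean the name will be absent, and the batch number could identify the product.
- **The work is not nil.** In 6.4 the designated site person checks adherence through the diary, and weighing is the sponsor's task. Kit coding and a code-break list are new procedures.
- **The remark about bottle characteristics in 4.2 is ambiguous** in this translated text, so it cannot be said with certainty that the reason concerns Hyabak alone. Hyabak is, however, the only product named.

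None of this supplies a reason against coding the two sponsor products. A patient who is not told the product still knows less than one who reads its name, even if some can guess.

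**Conclusion.** The point holds as a cheap improvement. The plan gives no stated reason that prevents masking Humylub against Lagricel, and their descriptions and regimen suggest that it is feasible. The gain is protection against differential bias in a patient-reported primary outcome, in one of two primary comparisons, and in subjective sign grades. The instrument-read tear break-up time (7.4.4.4) is less exposed.

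The size of the bias is not known. The rates in the table show sensitivity under assumed shifts, an assumed comparator rate and a one-sided normal-approximation test; they do not estimate what will happen. A reader might also note that six patients out of 60 equal the 10-point margin (6/60 = 10%) and take that as the size of the problem. It only restates the margin: it measures no bias, and non-inferiority is normally judged on a confidence limit rather than a count.

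The conclusion depends on caps and printing matching closely enough, which the sponsor must confirm.

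**What to change.** Amend 4.2, 6.1 and 7.3 as follows.

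1. Confirm that the caps and printing of Humylub and Lagricel match or can be made to match. Supply both under the same coded trial label, with kit numbers from the assignment system. Code batch and expiry so that they meet the labelling rules without revealing the product, and keep a code-break list.
2. In all three arms, have existing site staff other than the slit-lamp grader hand out and collect bottles, and tell patients not to name their product to the grader. This masks sign grading as far as possible in every arm, including Hyabak.
3. Describe the design as masked between the two sponsor products and open to patients for Hyabak. State in the report that the two primary comparisons are masked differently and that masking between the sponsor products may be imperfect because they may feel different.

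The cost is modest labelling, kit-coding and code-break work and a reallocation of bottle handling at sites. No extra visits or patients are needed. If masking proves impracticable, 4.2 should give a reason that applies to Lagricel; step 2 can still be adopted.
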